30.4 Study Telephone Recruitment Script

Hi, this is [Study Staff Name] calling from Massachusetts General Hospital. How are you today?

A1. Self-referral call-back: Thank you for reaching out to our study team regarding your interest in the STRIDE study. I would be happy to give you a brief overview of the study if you have a few minutes. Is now a good time?

IF YES: Continue to Section B.

IF NO: Is there a better time in the coming days I could give you a call back? [Continue to Section F.]

A2. Recruitment call: I am calling regarding a research study you might be eligible for and may have received a study flyer for while in-clinic last. Is now a good time that I could give you a brief overview of the study?

IF YES: Continue to Section B.

IF NO: Is there a better time in the coming days I could give you a call back? [Continue to Section F.]

B. Study Description

This study offers a program for women who are taking a hormonal therapy and consists of 6 weekly, small-group, virtual visits with a cancer center clinician to address any concerns or challenges you may be experiencing while taking this medication. Your oncologist said it would be alright if we speak with you about this study. These visits would take place over a secure videoconferencing software with a few other breast cancer survivors who are also taking hormonal therapy. Does this sound like something you might be interested in?

IF YES: Continue to Section C.

IF NO: Continue to Section F.

C. Eligibility Screening

Thank you for your interest; so, I have a few initial questions we like to ask to get a sense of if this study might be a good fit for you. All of these questions are optional and completely confidential.

Each question is scored on a scale of 0-10. The first question is, on a scale of 0 being not bothered at all to ten being extremely bothered, how bothered are you by side effects from your hormonal therapy?

My next question is, on a scale of 0 being not upset at all to ten being extremely upset, how upset are you by having to take hormonal therapy?

My last question is, on a scale of 0 being not difficult at all to 10 being extremely difficult, how difficult is it for you to take your hormonal therapy medication every day?

IF A SCORE OF 4 OR ABOVE ON ONE OR MORE: Thank you for going through those questions with me. It sounds like you would be a good fit for this study. The next step is to go through the consent form, which I can send you over email. What is the best email address to send it to?

IF A SCORE OF 3 OR LESS ON ALL THREE: Thank you for going through those questions with me. It sounds like you are doing well with taking the hormonal therapy medication right now and you screen out for the study. Would it be alright if I were to check in with you at some point in the future to see how you're doing?

IF YES: [Collect best contact information and thank for their time], continue to Part E

IF NO: Thank you for speaking with me today. You are always welcome to reach out if you have any questions about anything we spoke about today, but we will not reach out in the future. Continue to Part E.

D. Consent Form Access and the Informed Consent Discussion

Okay, I have sent the consent form to the email you provided. You should expect an email with the subject line "MGH STRIDE Study." This email will be sent from me and will include a link at the bottom. When you receive this email, please click this link to be directed to the consent form. The portal will prompt you to enter your full name and birthday to verify who you are to see the consent form.

[Informed Consent Discussion]

E. Not Interested, Refusal, Paper-Consent Preference, Ineligible Outcome

Thank you so much for your time today. Please feel free reach out with any questions or concerns related to the study.

30.5 Partners Rally Recruitment Advertisement

Headline: STRIDE: Symptom-Targeted Randomized Intervention for Distress on Endocrine Therapy

Summary (240 characters): If you were diagnosed with breast cancer and are currently taking a hormonal therapy, you may be eligible to participate in this research study. Participants are randomized to complete a 6-week, small-group, virtual intervention.

Project Title: Symptom-Targeted Randomized Intervention for Distress and Adherence to Adjuvant Endocrine Therapy (STRIDE) among Breast Cancer Survivors: A pilot feasibility trial

Categories: Breast Cancer, Cancer, Medicines

Project Image:

CT.gov Identifier: To be assigned

Funding Source: NIH

Institutions conducting research: MGH, Newton-Wellesley, MGH North Shore, MGH Waltham

IRB Organization: DF/HCC Dana Farber Cancer Institute

Recruitment start date: 2/1/2019

Recruitment end date: 5/1/2022

What are you studying?

We are studying the feasibility and effectiveness of a tailored program for women currently taking hormonal therapy for breast cancer to reduce distress and improve side effect management and adherence.

Why is it important?

A variety of challenges can arise around taking hormonal therapy, which can interfere with daily living and ability to take the medication. This program will allow women to explore and manage these concerns in a small-group with other breast cancer survivors and a cancer center clinician.

STRIDE

Symptom-Targeted Randomized Intervention for Distress on Endocrine Therapy

The MGH Cancer Outcomes Research Program is conducting a research study to support women taking a hormonal therapy after breast cancer treatment.

If you:

- ❖ Are at least 21 years old
- ❖ Have completed treatment for breast cancer
- ❖ Are currently taking and within 3 years of starting medication, such as Tamoxifen, Arimidex, Letrozole, Exemestane

You may be eligible to participate in a small-group, virtual intervention to manage side effects, decrease distress, and improve adherence to hormonal therapy.

If you would like to learn more about this research study, please tell your oncologist or contact the study coordinator, [name] or [name], at **[contact]** or at **[contact]** or **[contact]**.

Thank you for considering our research study! You will be helping us gather important information about a program that may help other patients in the future.

CANCER
OUTCOMES
RESEARCH

MASSACHUSETTS
GENERAL HOSPITAL
CANCER CENTER

30.7 Study Recruitment Voicemail Script

Hi, this is [study staff contact] calling from Massachusetts General Hospital. I am calling to get in contact with [patient name] about a program you may be interested in. Please give me a call back when you have the chance. You may reach me at [study staff contact information]. Thank you.

30.8 Study Randomization Scheme

Elevated				Arm B	
Elevated				Arm C	
Elevated				Arm C	
Elevated				Arm B	
Elevated				Arm C	
Elevated				Arm B	
Elevated				Arm C	
Elevated				Arm B	
Elevated				Arm C	
Elevated				Arm B	
Elevated				Arm C	
Elevated				Arm B	
Elevated				Arm B	
Elevated				Arm C	
Elevated				Arm B	
Elevated				Arm C	
Elevated				Arm C	
Elevated				Arm B	
Elevated				Arm C	
Elevated				Arm C	
Elevated				Arm B	
Elevated				Arm C	
Elevated				Arm B	
Elevated				Arm B	
Elevated				Arm C	

Randomization sheet for 18-603 - Not Elevated Distress				
Symptom Targeted Randomized Intervention for Distress and Adherence to Adjuvant Endocrine Therapy among Breast Cancer Survivors				
Stratification factors: Distress (elevated or not elevated)				
Treatment codes				
Arm B:	Intervention			
Arm C:	Control			
Distress level	Patient name	Sequence no.	Date entered	Treatment assignment
Not elevated				Arm C
Not elevated				Arm C
Not elevated				Arm B
Not elevated				Arm B
Not elevated				Arm B
Not elevated				Arm C
Not elevated				Arm B
Not elevated				Arm C
Not elevated				Arm B

Not elevated				Arm C	
Not elevated				Arm C	
Not elevated				Arm B	

30.9 Session Rating Form

Session 1 Your study ID _____
Please rate the following 5 items on a scale from 1 (Not at all) to 10 (Extremely so)

1. How enjoyable was today's session? _____
2. How convenient was today's session? _____
3. How helpful was today's session? _____
4. How likely are you to use skills/information from today's session in the future? _____
5. How would you rate your overall satisfaction with today's session? _____

Session 2 Your study ID _____
Please rate the following 5 items on a scale from 1 (Not at all) to 5 (Very much)

1. How enjoyable was today's session? _____
2. How convenient was today's session? _____
3. How helpful was today's session? _____
4. How likely are you to use skills/information from today's session in the future? _____
5. How would you rate your overall satisfaction with today's session? _____

Session 3 Your study ID _____
Please rate the following 5 items on a scale from 1 (Not at all) to 5 (Very much)

1. How enjoyable was today's session? _____
2. How convenient was today's session? _____
3. How helpful was today's session? _____
4. How likely are you to use skills/information from today's session in the future? _____
5. How would you rate your overall satisfaction with today's session? _____

Session 4 Your study ID _____
Please rate the following 5 items on a scale from 1 (Not at all) to 5 (Very much)

1. How enjoyable was today's session? _____
2. How convenient was today's session? _____
3. How helpful was today's session? _____
4. How likely are you to use skills/information from today's session in the future? _____
5. How would you rate your overall satisfaction with today's session? _____

Session 5 Your study ID _____
Please rate the following 5 items on a scale from 1 (Not at all) to 5 (Very much)

1. How enjoyable was today's session? _____
2. How convenient was today's session? _____
3. How helpful was today's session? _____
4. How likely are you to use skills/information from today's session in the future? _____
5. How would you rate your overall satisfaction with today's session? _____

30.10 Semi-Structured Interview Script

Introduction

Hello, my name is _____. You have been asked to participate in this interview to share your experiences going through the STRIDE program. I will ask you a variety of questions about your experiences during the study. I greatly appreciate your willingness to participate in this study.

This interview will take 15-30 minutes.

Everything that you share with me today is confidential, and your answers will not affect your future participation in studies or your access to medical services.

There are no right or wrong answers to these questions. It is very important for us to hear your thoughts and feelings on the program, so we can improve it for the future.

I would like to audio-record this interview because I will not be able to write all this information down. The interview will be transcribed word for word and will allow us to capture your thoughts and feelings in your own words. No identifying information, such as your name or names of others, will be included in the transcript. Additionally, your responses will never be reviewed individually. Responses will be collected and combined from all participants for feedback to the study team.

Do I have permission to record this interview?

Before we start, do you have any questions about what we are doing here today?

(TURN ON RECORDER)

1. How did you feel about the number of STRIDE sessions?
2. How did you feel about how long each session lasted?
3. How satisfied were you with the information you received?
4. Have you used any of the skills that you learned?
 Probe: Relaxation skills, skills for coping with symptoms, etc.
5. How did you feel about the group structure?
6. How did you feel about the individual structure?
7. How did you feel about the videoconference?
8. How did you feel about attending sessions in person?
9. How did you feel about storing your medication in the bottle that we gave you?
 Probe: Was this difficult?
 Probe: Did anything get in your way of storing the medication there?
10. How did you feel about the packet of questionnaires?
 Probe: Too long?
 Probe: Was anything confusing?
11. How did you feel about the number of times we asked you to complete the questionnaires?
12. How did you feel about the phone check-ins that we did after the sessions?
13. Do you have any suggestions for how to improve our program?
14. Did anything get in the way of you being able to participate?
15. Would you recommend this to other women on hormonal therapy?

Semi-structured Interview Guide:

Introduction

Nice to speak with you, my name is _____ and thank you for being a part of this study! As a reminder, in (fill in) year, you participated in a study that was evaluating a program to support women on hormonal therapies after breast cancer. Now, we are conducting this final interview to understand how we can improve our study activities to be more sensitive and relevant for people from all cultural, racial, and ethnic backgrounds. We are hoping to expand this study to include more women who identify as Black, Latina, or Asian women, and want to make sure the program meets the needs of women from every background,

There are no right or wrong answers, and everything that you share is completely confidential. None of your answers will get back to your doctors or nurses, and your answers will not affect your future participation in studies or the care you receive here at MGH. We are asking all women the same questions, because the goal of this interview is to understand how we can make sure this program is relevant for women of different races, ethnicities, and cultures. So, I will also ask you a few questions about the program, whether you believe it would be helpful to women in the future, and if you have any concerns or suggestions to improve it.

The interview will take about 15-30 minutes. I will be moving us along so that we make sure to cover all of the questions.

As a reminder, I will be audio-recording this interview to make sure that I capture your thoughts and feelings in your own words. We will destroy the recording once we have transcribed it and no identifying information, such as your name or names of others, will be included in the transcript. Do I have permission to record this interview?

Do you have any questions before we start?

(START RECORDING)

1. Can you share with me, how do you identify yourself (for example, as a Black Hispanic woman, as a Chinese American)?
2. Was there anything that got in the way of you participating in this study?
3. Was there anything that got in your way of participating that relates to your race, ethnicity, culture, or other way you identify yourself?
 - a. Offer examples: were the questions in the survey relevant to you? were the examples in the workbook relevant to you (only for intervention participants)?
4. What did you like about this study/program?
5. What did you dislike about this study/program?
6. Was there anything related to your race, ethnicity, or cultural background that got in the way of you taking your hormonal therapy medication every day?
 - a. Offer example: some groups might question how well these medications work, some may have less trust in their doctors and nurses.
7. Was there anything related to your race, ethnicity, or cultural background that got in the way of your ability to manage side effects from the medication?
 - a. Offer example: some groups might question how well these medications work, some may have less trust in their doctors and nurses.
8. Have you been able to talk with your doctors and nurses about any issues you have had with your hormonal therapy?
9. Do you feel that your experience, or concerns about this medication, are the same or different from other women in a similar position?
 - a. Probe: how about women from different backgrounds?
10. How do you think we could make this program meet the needs of women of different backgrounds?
11. If we translated the program into Spanish, do you foresee any issues with Spanish-speaking women participating?
12. Is there anything you can think of, that could help support you to continue to take the medication?

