14.3 Reaction Management

The consent form will include all the study procedures, information about potential risks and benefits of participation, and information regarding whom the participant can contact for further questions. It also will state that participation is voluntary, that participants can refuse to answer any question, that they can withdraw from the study at any time, and that study participation is in no way related to their medical care. All study staff will complete the required human subjects training before they can work on any human subject aspects of the study.

If a participant expresses distress during the psychological intervention visits or exit interviews, they will be reassured by the clinician or study staff member conducting the intervention visit or interview that they can stop at any time and that they do not need to continue participating in content or answer interview questions which they find upsetting. They will also be reminded that study participation is voluntary. If participants remain distressed, they will be offered an opportunity to meet with a psychologist in the Psychiatric Oncology Service at the MGH Cancer Center to help address their distress.

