For all participant assessments given throughout the study, study staff will review assessments upon receipt from participants for completion and to assess distress. On the HADS, patients who endorse ≥ 11 on even items for a more severe range for depression will be called by qualified study staff (e.g., [name], a licensed clinical psychologist, [name], a licensed clinical psychologist, [name], a licensed clinical social worker, as well as qualified clinical psychology practicum students and fellows). If a participant completes the distress assessment online through the secure REDCap portal, a study staff member will check the responses and notify the PI for follow-up if needed within 72 hours of assessment completion. If a participant completes assessments on paper, study staff will check the responses and notify the PI for follow-up if needed within 72 hours of receipt. If the patient needs further outpatient services for depression, including pharmacotherapy, or is at risk for self-harm requiring hospitalization, study staff will make the necessary referrals for treatment. For example, for patients who are distressed but in no danger to self or others, study staff will refer either to the MGH Oncology Social Work Service or to the MGH Outpatient Psychiatry Department [contact]), including the Cognitive-Behavioral Therapy Program. If suicidality or risk of harm to others is otherwise discovered at any study visit, the participant will be referred to appropriate services. Specifically, in the case that hospitalization is required, study staff will contact and escort the patient to the MGH Acute Psychiatry Service [contact]), with the aid of the MGH Police & Security if necessary [contact]). If a referral for outpatient services is made, or the patient requires escort to the MGH Acute Psychiatry Service, study staff will notify the health care team, including the primary oncologist.

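### The RCT exit-interview script promises that no answer will reach a woman's clinicians and makes no exception for the notification that section 14.3 requires after a referral or escort

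*Combined protocol and SAP*

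**What the plan says.** Women in the RCT who identify with a racial or ethnic minority are offered a short qualitative exit interview, whichever arm they were in (section 3.2). Section 9.3 assigns it to a staff member who did not deliver the intervention. The script is printed after the run-in script and listed in section 30.0 as Appendix 30.11. Its introduction says that "everything that you share is completely confidential" and, in the next sentence, "None of your answers will get back to your doctors or nurses". Neither the introduction nor the questions set any limit on this.

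Section 14.3 (Reaction Management) has a paragraph that begins "If a participant expresses distress during the psychological intervention visits or exit interviews". It provides for reassurance and a reminder that she may stop. For a woman who stays distressed, it says that "they will be offered an opportunity to meet with a psychologist in the Psychiatric Oncology Service".

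The next paragraph opens with the review of questionnaire responses and then widens: "If suicidality or risk of harm to others is otherwise discovered at any study visit, the participant will be referred to appropriate services". It closes with a duty that depends on a referral or escort. In that event, "study staff will notify the health care team, including the primary oncologist".

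**The concern.** The script is what the woman hears immediately before she speaks. It tells her that nothing will go back to the people treating her. Section 14.3 gives the same study staff a duty to contact those people in defined circumstances, and it counts exit interviews among the settings where distress may surface. An interviewer who reads the script as written, and then hears something that leads to a referral or escort, has given an assurance that the protocol does not let staff keep.

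What is at stake is whether participants are told the truth about the limits of confidentiality. If the case arose, a woman would have disclosed something on an assurance that did not hold, or staff would have to choose between the script and section 14.3. The first would be awkward in an interview meant to learn about cultural relevance, where the guide itself offers lower trust in doctors and nurses as an example.

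**Working it through.** No arithmetic applies. The check is a comparison of texts.

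1. *Is the promise unconditional?* Yes. The RCT script speaks of complete confidentiality and separately rules out any answer reaching doctors or nurses. No exception for safety appears in the introduction or in the 12 questions.

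2. *Does section 14.3 reach exit interviews?* Yes for distress, because it names them. For suicidality or risk to others, the trigger is discovery at any study visit. The protocol does not say that an exit interview falls outside that phrase.

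3. *Is the notification mandatory?* Yes, once its condition is met: "If a referral for outpatient services is made, or the patient requires escort to the MGH Acute Psychiatry Service, study staff will notify". The sentence is not tied to a questionnaire result or to a particular setting.

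4. *Do the recipients overlap?* Yes. The script excludes the woman's doctors and nurses. Section 14.3 names her health care team and primary oncologist.

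5. *When do the texts collide?* Three things must happen in turn: a disclosure in the interview, a referral for outpatient services or an escort because of it, and the resulting notice to the care team. Without the second there is no notification duty and no conflict.

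6. *How often would that happen?* The documents do not allow an estimate. They give neither the number of RCT exit interviews nor any rate of disclosures that would lead to referral or escort. Active suicidal ideation was an exclusion at entry (Table 1), and the questions concern identity, cultural relevance, barriers and side effects. Both suggest that the event would be uncommon.

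**The case against.** The strongest reply is that the two texts can be read together. The paragraph of section 14.3 written for interviews provides only reassurance, the right to stop and the offer of a psychologist. The notification sentence sits in the following paragraph, which starts from questionnaire review, and it requires notice of a referral or escort without saying that the answers themselves are passed on. This narrows the conflict but does not remove it. The wording about any study visit is general. An oncologist who is told of a referral prompted by the interview learns in substance what was disclosed, and the promise of complete confidentiality excludes even that.

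A second reply is that the consent form may state the exception. Those pages were not available, so this can be neither confirmed nor counted against the plan. Even if the exception is there, an unqualified oral assurance given just before the interview would contradict it.

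A third reply is that nothing suggests an interviewer would hold back a required notice because of a scripted introduction. That is fair. The point that stands is the accuracy of what participants are told.

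Several stronger readings are tempting, and the documents do not support them:

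- *That one of the two texts is bound to be broken.* This holds only if a referral or escort follows. Reporting side effects, missed pills or mistrust triggers nothing in section 14.3. Nor does the protocol say that the offer of a psychologist counts as an outpatient referral.
- *That the run-in script has the same fault.* It says "Everything that you share with me today is confidential" but makes no promise about doctors or nurses, and the preliminary-studies text in section 2.0 reports the five-person run-in as finished.
- *That serious adverse event reporting in section 12.1 breaks the promise.* Those reports go to the PI, the IRB and federal agencies, not to treating clinicians. They bear at most on the broader claim of complete confidentiality.
- *That a probability can be attached.* The 12% rate of elevated depression in section 2.0 comes from women with breast cancer in a study of oral chemotherapy, and any number of interviewees would have to be assumed. Elevated depression is not itself an interview trigger: the HADS call rule applies to questionnaires, and Table 3 schedules no HADS at the exit interview.
- *That the entry score of 4 or more shows current distress.* Those items ask about bother from side effects, upset at having to take therapy and difficulty taking it daily. They were asked at entry, whereas the interview follows completed participation.

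**Conclusion.** The concern holds in a limited form. The RCT exit-interview script makes an unqualified promise that staff could not keep while following section 14.3 if an interview disclosure led to an outpatient referral or an escort to acute psychiatry. The contradiction is in the text and needs no figure. Its frequency is unknown and probably low, and no endpoint, sample size or analysis is touched.

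The conclusion rests on two assumptions. One is that section 14.3 is meant to apply to exit interviews in full, which its wording supports but does not put beyond doubt. The other is that the script is read as printed. It does not depend on what the consent form says. The correction is worth making because a failed assurance would be serious for the woman concerned and the change is small.

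**What to change.** Reconcile the RCT exit-interview script with section 14.3. Replace the unconditional promise with one sentence, read before recording starts, that states the exception section 14.3 already makes for notifying the care team after a referral or escort. Check that the sentence matches the confidentiality wording in the consent form. If the sponsor does not intend the notification duty to cover exit interviews, section 14.3 should say so. That decision belongs to the sponsor, and this point takes no view on what the clinical rule should be.

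The cost is one sentence and a minor amendment, with no new procedure, data item or participant. The downside is that a few women may be slightly more guarded in what they say.
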